
13 Appendix 1: Sample Log table – all matrices

15 Appendix 3: Liver event definitions and follow-up requirements

	Definition / threshold		
Adverse event of special interest			
Laboratory values	ALT or AST > 3 x ULN		
	ALP > 2 x ULN		
	TBL > 1.5 x ULN		
Medically significant event (SAE)			
Laboratory values	ALT or AST > 5 x ULN (with or without TBL > 2 x ULN [mainly conjugated fraction])		
	ALP > 5 x ULN (with or without TBL > 2 x ULN [mainly conjugated fraction])		
	TBL > 3 x ULN		
	Potential Hy's Law cases (defined as ALT/AST > 3 x ULN and TBL > 2 x ULN [mainly conjugated fraction] without notable increase in ALP to > 2 x ULN)		
Adverse events	Any clinical event of jaundice (or equivalent term)		
	ALT or AST > 3 x ULN accompanied by general malaise, fatigue, abdominal pain, nausea, or vomiting, or rash with eosinophilia		
	Any event that links to a preferred term (PT) in the MedDRA dictionary falling under the SMQ sub-module "Drug-related hepatic disorders – severe events only"* or any "Hy's law case" PT		

conditions; the non-infectious hepatitis; the benign, malignant and unspecified liver neoplasms

Table 15-1Liver Event Definitions

Criteria	Event type	Actions required	Follow-up monitoring
Potential Hy's Law case ^a	Medically significant	Hospitalize, if clinically appropriate Report to Novartis as an SAE Establish causality	ALT, AST, TBL, Alb, PT, ALP and γGT until resolution ^c (frequency at investigator discretion)
ALT or AST			
> 8 x ULN	Medically significant	Repeat LFT within 48 hours Hospitalize if clinically appropriate Report to Novartis as an SAE Establish causality	ALT, AST, TBL, Alb, PT, ALP and γGT until resolution ^c (frequency at investigator discretion)
> 5 to ≤ 8 x ULN	Medically significant	Repeat LFT within 48 hours If elevation persists for more than 2 weeks , discontinue the study drug Report to Novartis as an SAE Establish causality	ALT, AST, TBL, Alb, PT, ALP and γGT until resolution ^c (frequency at investigator discretion)
> 3 x ULN accompanied by symptoms ^b	Medically significant	Hospitalize if clinically appropriate Report to Novartis as an SAE Establish causality	ALT, AST, TBL, Alb, PT, ALP and γGT until resolution ^c (frequency at investigator discretion)
> 3 to ≤ 5 x ULN (patient is asymptomatic)	AESI	Central laboratory to report to Investigator & Novartis Repeat LFT once or twice in the week If elevation persists, establish causality	Investigator discretion Monitor LFT within 1 to 4 weeks or at next visit
≤ 3 x ULN (patient is asymptomatic)	N/A	Repeat LFT at next visit	
ALP (isolated)			
> 5 x ULN	Medically significant	Repeat LFT within 48 hours If elevation persists, report to Novartis as an SAE Establish causality	Investigator discretion Monitor LFT within 1 to 4 weeks or at next visit
> 2 to ≤5 x ULN (patient is asymptomatic)	AESI	Central laboratory to report to Investigator & Novartis Repeat LFT once or twice in the week If elevation persists, establish causality	Investigator discretion Monitor LFT within 1 to 4 weeks or at next visit
≤ 2 x UL N (patient is asymptomatic)	N/A	Repeat LFT at next visit	

Table 15-2 Liver Event Follow Up Requirements

Novartis Amended Protocol Version v06 (Clean)

Criteria	Event type	Actions required	Follow-up monitoring
TBL (isolated)			
> 3 x ULN	Medically significant	Repeat LFT within 48 hours	ALT, AST, TBL, Alb, PT, ALP and γGT until resolution ^c (frequency at investigator discretion)
		Hospitalize if clinically appropriate	
		Report to Novartis as an SAE Establish causality	Test for hemolysis (e.g., reticulocytes, haptoglobin, unconjugated [indirect] bilirubin)
> 1.5 to ≤ 3 x ULN AESI (patient is asymptomatic)	AESI	Central laboratory to report to Novartis	investigator discretion Monitor LFT within 1 to 4 weeks or at next visit
		Repeat LFT once or twice in the week	
		If elevation persists, establish causality	
≤ 1.5 x ULN	N/A	Repeat LFT at next visit	
(patient is asymptomatic)			
Preferred terms			
Jaundice	Medically significant	Hospitalize the patient	ALT, AST, TBL, Alb, PT,
		Report to Novartis as an SAE Establish causality	ALP and γGT until resolution ^c (frequency at investigator discretion)
"Drug-related hepatic disorders - severe events only" SMQ AE	Medically significant		Investigator discretion
		hospitalization if clinically appropriate	
		Report to Novartis as an SAE	
		Establish causality	

a Elevated ALT/AST > 3 x ULN and TBL > 2 x ULN but with no notable increase in ALP to > 2 x ULN

^b General malaise, fatigue, abdominal pain, nausea, or vomiting, rash with eosinophilia

^c Resolution is defined as an outcome of one of the following: return to baseline values, stable values at three subsequent monitoring visits at least 2 weeks apart, remain at elevated level after a maximum of 6 months, liver transplantation, and death.

1.1 Scope

The RAP documents contain detailed information to aid the production of Statistics & Programming input into the Clinical Study Report (CSR) for trial “**CCGF166X2201**”.

Module 3 (M3) provides the description of the statistical methodology used to analyze the data, **Module 7 (M7)** details the presentation of the data, including shells of summary tables, figures and listings, and **Module 8 (M8)** contains programming specifications e.g. for derived variables and derived datasets, to support the creation of CSR outputs.

1.2 Changes to RAP documentation (M3)

Refer to corresponding guidances and Translational Sciences (TSc) RAP Addendum template for detailed information on the requirements of documenting changes to RAP documentation.

For the statistical methodology (M3), any major changes occurring before database lock to the statistical methodology should be reflected in the RAP M3 documentation via version control (new document version to be approved by the trial team as the original module).

Major changes include, but are not limited to, changes in protocol that affect study design and statistical methodology.

Minor changes to the RAP M3 documentation can be captured e.g. by a study note to file / note in RAP Addendum or within the CSR itself. Minor changes include, but are not limited to, change in statistical model. Corrections of typographical errors or modification of spelling (from English to American, for example) do not need to be incorporated into the RAP M3 documentation.

2 Study objectives and design

2.1 Study objectives

2.1.1 Primary objectives

- To assess the safety and tolerability of Intra-labyrinthine (IL) CGF166
- To assess the efficacy of IL CGF166 as determined by the change in pure tone audiometry compared to pretreatment values

2.1.2 Secondary objectives

- To assess the efficacy of CGF166 as determined by the change in otoacoustic emission testing compared to pretreatment values
- To assess the efficacy of CGF166 as determined by the change in brainstem auditory evoked responses (BAER) compared to pretreatment values
- To assess the efficacy of CGF166 in regenerating vestibular function as determined by the change in caloric nystagmography and vestibulo-ocular reflex (VOR) phase compared to pretreatment values
- To compare the changes in auditory functions (speech recognition) and vestibular functions before and after IL infusion of CGF166 between the study ear and the contralateral ear

2.1.3 Exploratory objectives

Commercially Confidential Information

2.2 Study design and treatment

The current three part study utilizes an open label, single dose design for the investigation of CGF166 and will be conducted in multiple centers. Part A, B and C will be conducted in a sequential manner.

The current study will evaluate the safety, tolerability, and potential efficacy of CGF166 and the associated delivery procedures in patients with severe-to-profound bilateral hearing loss with intact vestibular function in the non-operative ear. Patients are required to have documented non-fluctuating hearing loss.

Commercially Confidential Information

Part A

Part A will include a safety and tolerability cohort (N=3). Patient dosing will be staggered; dosing the next patient in a cohort will be based on a safety data review including all data available through 4 weeks post-dose of the previously dosed patient(s).

Part B

Part B will include a volumetric escalation design to evaluate infusion volumes of the same CGF166 concentration Commercially Confidential Information in 4 cohorts of patients (N=3/cohort; total of 12 patients).

Each subsequent cohort will be dosed only after the volume delivered in the prior cohort is deemed to be safe and tolerable as determined by the dose safety review meeting based on safety data review of the complete previous cohort including all data through 4 weeks post-dose.

Safety review meetings will be organized to evaluate available safety data and to determine if it is appropriate to escalate to the next infusion volume.

Part C

Once the highest safe and tolerable volume is determined in previous cohorts, it will be used for IL-infusion in Part C patients. A total of 20 patients, possibly increasing to 30 based on a sample size re-estimation after a data review of the Part A and B (cohorts 1-5), will be required for Part C of the current study.

3 First interpretable results (FIR)

Commercially Confidential Information

4 Interim analyses

Commercially Confidential Information

5 Statistical methods: Analysis sets

All patients that received study drug and with no protocol deviations with relevant impact on safety will be included in the safety analysis set.

Commercially Confidential Information

Commercially Confidential Information

6 Statistical methods for Pharmacokinetic (PK) parameters

Not applicable.

7 Statistical methods for Pharmacodynamic (PD) parameters

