3.1 Study design

This non-confirmatory three part study utilizes an open label, single dose, sequential cohort design for the investigation of CGF166 and will be conducted in multiple centers.

The current study will evaluate the safety, tolerability, and potential efficacy of CGF166 and the associated delivery procedures in patients with severe-to-profound bilateral or unilateral hearing loss with intact vestibular function in the non-operative ear. Patients are required to have documented non-fluctuating severe-to-profound bilateral or unilateral hearing loss prior to enrollment. A maximum of 22 patients will be enrolled in this 3 Part, 5 cohort trial (Figure 3-1).

Novartis Amended Protocol Version v06 (Clean) Confidential

Page 40 Protocol No. CCGF166X2201

Part A

Part A will assess the safety and tolerability as well as potential efficacy following a single IL dose of 20 uL of CGF166 concentration Commercially Confidential Patient enrollment will be staggered so that a safety data review can be done after each treated patient (~4 weeks after treatment) prior to dosing each subsequent patient.

Part B

Part B will include a volumetric escalation design to evaluate up to 3 infusion volumes (between 20 and 60 μ L) of the same CGF166 concentration^{Commercially Confidential} 3 cohorts of patients (n=3/cohort; total of 9 patients). All dose volumes are subject to change based on trial safety data.

Each subsequent cohort will be dosed only after the volume delivered in the prior cohort is deemed to be safe and tolerable as determined by the Drug Safety Monitoring board (DSMB). The DSMB will consist of internal Novartis personnel as well as at least one external subject matter expert who is not serving as an investigator or otherwise privy to trial data. The membership and workings of the DSMB will be detailed in the DSMB Charter. In addition, the scheduling and dosing of the first patient in each cohort will be staggered to allow at least a four week interval in between treating the remaining 2 patients in each cohort.

Part C

Considering the preliminary overall review of the data including changes observed in audiometry for patients from Cohort 1 through Cohort 4, the DSMB endorsed the team's proposal that $30 \ \mu L$ is the maximum tolerated dose (volume) observed in the study.

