5.2 Treatment arms

Patients will be assigned to one of the 5 cohorts. Part A and Part B of the study have been completed; dose volumes administered reflect the study treatment for each cohort including planned dose volume for Part C of the study (see Table 5-1 for estimated viral particle delivery quantity and normalized doses estimates).

Study treatments are defined as:

- Part A:
 - Cohort 1: single dose of 20 µL CGF166
- Part B:
 - Cohort 2: single dose of 40 or 30 µL CGF166
 - Cohort 3: single dose of 40 µL CGF166
 - Cohort 4: single dose of 60 µL CGF166
- Part C:
 - Cohort 5: single dose of 30 µL @ 10 µL/minCGF166

Commercially Confidential Information

Confidential

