9.1 Analysis sets

For all analysis sets, patients will be analyzed according to the study treatment(s) received.

The safety analysis set will include all patients that received any study drug.

The PD analysis set will include all patients with available PD data and no protocol deviations with relevant impact on PD data.

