9.4.2 Statistical model, hypothesis, and method of analysis

Tone thresholds will be analyzed for each frequency tested separately.

For pure tone audiometry, a measure that depends on a patient being able to hear a tone, the following imputation will be done: If a patient is unable to hear the tone at a specific frequency it can be inferred that the threshold value exceeds the upper limit of the machine. In this case the value will be imputed to 5dB above the upper limit of the machine.

All pure tone audiometry air conduction threshold data will be listed and graphically displayed by patient, infusion volume, frequency, and visit/time. Summary statistics will be provided by infusion volume, frequency, ear and visit/time. Change from baseline of the thresholds (mean of screening and baseline visit) will also be summarized by infusion volume, frequency, ear and visit/time.

In addition, safety and tolerability is a co-primary endpoint, and will be analyzed as in Section 9.5.2 (Safety).

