8.1 Safety

The second primary objective is to assess the safety and tolerability of IL CGF166.

Vital signs

All vital signs data will be listed by infusion volume, patient and visit/time and if ranges are available abnormalities (and relevant orthostatic changes) will be flagged. Summary statistics will be provided by infusion volume and visit/time.

ECG evaluations

All ECG data will be listed by infusion volume, patient and visit/time, abnormalities will be flagged. Summary statistics will be provided by infusion volume and visit/time.

Clinical laboratory evaluations

All laboratory data will be listed by infusion volume, patient, and visit/time and if normal ranges are available abnormalities will be flagged. Summary statistics will be provided by infusion volume and visit/time.

Adverse events

All information obtained on adverse events will be displayed by infusion volume and patient.

The number and percentage of patients with adverse events will be tabulated by body system and preferred term with a breakdown by infusion volume where applicable. A patient with multiple adverse events within a body system is only counted towards the total of this body system.

Magnetic Resonance Imaging (MRI)

An MRI will be used to assess the structural integrity of the inner ear at screening and following treatment. The MRI data will be listed by infusion volume, patient and visit.

Commercially Confidential Information

Columbia-Suicide Severity Rating Scale (C-SSRS)

The C-SSRS data will be listed by infusion volume, patient and visit/time.

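### The SAP's safety analysis set can drop dosed patients for protocol deviations, whereas Protocol 9.1 includes everyone who was dosed

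*SAP*

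**What the plan says.** SAP section 5 (Statistical methods: Analysis sets) gives the safety population two conditions, dosing and the absence of a certain kind of deviation: "All patients that received study drug and with no protocol deviations with relevant impact on safety will be included in the safety analysis set". Redacted text follows that sentence.

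Protocol 9.1 has only the dosing condition: "The safety analysis set will include all patients that received any study drug". It also says that patients are analysed by the treatment they received. A deviation condition does appear in Protocol 9.1, but only for the pharmacodynamic set: "The PD analysis set will include all patients with available PD data and no protocol deviations with relevant impact on PD data".

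On the role of safety, Protocol 9.4.2 states that "safety and tolerability is a co-primary endpoint", and SAP 8.1 calls it the second primary objective.

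On reporting, SAP 8.1 plans a summary table: "The number and percentage of patients with adverse events will be tabulated by body system and preferred term with a breakdown by infusion volume" (the SAP adds that the breakdown applies where applicable). It also plans a patient-level display: "All information obtained on adverse events will be displayed by infusion volume and patient". The visible text of SAP section 8 does not say which analysis set these outputs use.

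**The concern.** The two definitions cannot both govern the same analysis. A safety population normally contains everyone exposed, because its purpose is to describe what happened to those who got the treatment. The SAP's extra condition selects on relevance to safety, so it could remove patients who are informative about that objective. The trial is open label, so whether a deviation qualifies could be judged with the patient's outcome already known. The visible text gives no criterion for that judgement.

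At stake are the adverse event counts, percentages and denominators for a co-primary objective. Protocol 9.5.2 also allows exact binomial intervals and a dose-related contrast test on adverse events, and both depend on who is counted. The bias could go either way: removing a patient who had an event lowers the rate, and removing one who did not raises it.

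**Working it through.** **1. The two rules side by side.**

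| | Dosed, no qualifying deviation | Dosed, qualifying deviation |
|---|---|---|
| Protocol 9.1 | in | in |
| SAP section 5 | in | out |

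The rules disagree in the last column. How a qualifying deviation is defined affects how many patients fall there, but does not remove the disagreement.

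**2. Is the protocol's wording deliberate?** It appears so. Protocol 9.1 applies a deviation filter to the pharmacodynamic set in the very next sentence and not to the safety set. Protocol 5.5.9 follows the same logic: a patient who needs a potent ototoxin may stay in the study but leaves the efficacy analysis, and no safety exclusion is stated.

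**3. Planned row sizes by infusion volume.** Neither document states a figure that depends on this point, so the only figure to reproduce is the total. Inputs: Part A has 3 patients; Part B has 3 cohorts of 3 (9 patients); Part C has 10 (Protocol 3.1). The sum is 3 + 9 + 10 = 22, which matches "A maximum of 22 patients will be enrolled in this 3 Part, 5 cohort trial".

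Volumes are in Protocol 5.2. One cohort is mixed: "Cohort 2: single dose of 40 or 30" µL. Let k be the number of cohort 2 patients given 30 µL (0 to 3, not stated).

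- 20 µL: 3
- 30 µL: 10 + k = 10 to 13
- 40 µL: 3 + (3 − k) = 3 to 6
- 60 µL: 3
- Total: 22 for every k

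**4. Effect of one exclusion.** With x events in n patients, removing one patient gives:

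- patient had the event: (x − 1)/(n − 1), a shift of −(n − x)/[n(n − 1)]
- patient did not: x/(n − 1), a shift of +x/[n(n − 1)]

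Over all possible x, the largest shift in either direction is 1/n. The documents give no event counts or deviation rates, so the x values below are assumed for illustration. The last column does not depend on them.

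| Row | n | Assumed rate | Excluded patient had event | Excluded patient did not | Largest shift, any x (points) |
|---|---|---|---|---|---|
| 20 µL, 60 µL (and 40 µL if k = 3) | 3 | 1/3 = 33.3% | 0/2 = 0% | 1/2 = 50.0% | ±33.3 |
| 40 µL if k = 0 | 6 | 1/6 = 16.7% | 0/5 = 0% | 1/5 = 20.0% | ±16.7 |
| 30 µL if k = 0 | 10 | 2/10 = 20.0% | 1/9 = 11.1% | 2/9 = 22.2% | ±10.0 |
| 30 µL if k = 3 | 13 | 2/13 = 15.4% | 1/12 = 8.3% | 2/12 = 16.7% | ±7.7 |
| All patients | 22 | 1/22 = 4.5% | 0/21 = 0% | 1/21 = 4.8% | ±4.5 |

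**5. Effect on exact 95% (Clopper-Pearson) intervals** when the only patient with the event is the one excluded:

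- cohort of 3: 1/3 (0.8% to 90.6%) becomes 0/2 (0% to 84.2%)
- Part C: 1/10 (0.3% to 44.5%) becomes 0/9 (0% to 33.6%)
- whole study: 1/22 (0.1% to 22.8%) becomes 0/21 (0% to 16.1%)

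The intervals are wide in any case. What changes materially is that an observed event disappears from the summary and the upper limit falls.

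**The case against.** The strongest reply accepts that the wording differs but disputes that it matters in practice.

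- **The harm is conditional.** A patient is lost only if some deviation qualifies, if it occurs in a dosed patient, and if the SAP 8.1 tables use this set. The redacted text after the definition, or the table shells and dataset specifications in Modules 7 and 8 (not supplied), might settle these points. This stands as a limit on what can be shown. It does not rescue the sentence, because a definition would only say which dosed patients are removed, and any such removal departs from Protocol 9.1.
- **The SAP may follow another protocol version.** SAP 2.2 has 4 Part B cohorts and 20 to 30 patients in Part C, hence 3 + 12 + 20 = 35 to 3 + 12 + 30 = 45 in total, against 22 in protocol v06. That may explain the mismatch but does not resolve it. SAP 1.2 classes protocol changes that affect design and methodology as major and calls for a new SAP version.
- **A correction may exist elsewhere.** SAP 1.2 lets minor changes be recorded in a note to file, an addendum or the study report. None is supplied, so this cannot be ruled out.
- **The trial is small, non-confirmatory and reported by patient.** Adverse events are displayed patient by patient. DSMB review, the stopping rules and SAE reporting are not visibly tied to this set. An omission from a summary table could therefore be noticed. This is fair and limits the harm, but the summary percentages would still rest on a population that the protocol does not define.
- **The row sizes are not certain.** The breakdown by volume is planned only where applicable. The figure of 22 is an enrolment maximum, and the protocol glossary defines enrolment at consent, so fewer may be dosed. The row sizes above are planned values.

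**Conclusion.** The concern holds. SAP section 5 states a rule that, followed as written, can leave dosed patients out of the safety population, contrary to Protocol 9.1, for a co-primary objective. The contradiction itself needs no assumption.

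Its practical size does rest on assumptions: that at least one dosed patient has a qualifying deviation, that the SAP 8.1 summaries use this set (the natural reading, given its name), and that planned cohort sizes are met. On that basis one exclusion can move an adverse event rate by up to 33 points in a row of 3, 8 to 10 points in the 30 µL row, and 4.5 points over 22 patients. The documents give no direction for the bias and no evidence that anyone was or would be excluded. Because the affected population belongs to a co-primary objective and the correction is nearly free, it should be made before database lock.

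**What to change.** 1. Replace the sentence in SAP section 5 with the protocol's definition, "The safety analysis set will include all patients that received any study drug", and state that patients are analysed by the treatment received.
2. State in SAP section 8 that the safety tables and listings use this set.
3. Preferably, flag protocol deviations in the safety listings so that readers can judge their influence. The contradiction is resolved without this step.
4. If a deviation-restricted set is wanted, write its criterion before database lock and use it only for a supplementary analysis.

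The cost is one sentence in section 5 and one cross-reference in section 8, made through the version control that SAP 1.2 already describes. No new data are needed. If the SAP is being brought into line with protocol v06 anyway, both edits belong in that update.
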